2 ETHICAL CONSIDERATIONS

2.1 Good Clinical Practice

This study will be conducted in accordance with Good Clinical Practice (GCP), as defined by the International Conference on Harmonisation (ICH) and in accordance with the ethical principles underlying European Union Directive 2001/20/EC and the United States Code of Federal Regulations, Title 21, Part 50 (21CFR50).

The study will be conducted in compliance with the protocol. The protocol and any amendments and the subject informed consent will receive Institutional Review Board/Independent Ethics Committee (IRB/IEC) approval/favorable opinion prior to initiation of the study.

All potential serious breaches must be reported to BMS immediately. A serious breach is a breach of the conditions and principles of GCP in connection with the study or the protocol, which is likely to affect, to a significant degree, the safety or physical or mental integrity of the subjects of the study or the scientific value of the study.

Personnel involved in conducting this study will be qualified by education, training, and experience to perform their respective tasks.

This study will not use the services of study personnel where sanctions have been invoked or where there has been scientific misconduct or fraud (eg, loss of medical licensure, debarment).

2.2 Institutional Review Board/Independent Ethics Committee

Before study initiation, the investigator must have written and dated approval/favorable opinion from the IRB/IEC for the protocol, consent form, subject recruitment materials (eg, advertisements), and any other written information to be provided to subjects. The investigator or BMS should also provide the IRB/IEC with a copy of the Investigator Brochure or product labeling information to be provided to subjects and any updates.

The investigator or BMS should provide the IRB/IEC with reports, updates and other information (eg, expedited safety reports, amendments, and administrative letters) according to regulatory requirements or institution procedures.

2.3 Informed Consent

Investigators must ensure that subjects are clearly and fully informed about the purpose, potential risks, and other critical issues regarding clinical studies in which they volunteer to participate.

In situations where consent cannot be given to subjects, their legally acceptable representatives as per country guidelines) are clearly and fully informed about the purpose, potential risks, and other critical issues regarding clinical studies in which the subject volunteers to participate.

BMS will provide the investigator with an appropriate (ie, Global or Local) sample informed consent form which will include all elements required by ICH, GCP and applicable regulatory requirements. The sample informed consent form will adhere to the ethical principles that have their origin in the Declaration of Helsinki.

Investigators must:

- 1) Provide a copy of the consent form and written information about the study in the language in which the subject is most proficient prior to clinical study participation. The language must be non-technical and easily understood.
- 2) Allow time necessary for subject or subject's legally acceptable representative to inquire about the details of the study.
- 3) Obtain an informed consent signed and personally dated by the subject or the subject's legally acceptable representative and by the person who conducted the informed consent discussion.
- 4) Obtain the IRB/IEC's written approval/favorable opinion of the written informed consent form and any other information to be provided to the subjects, prior to the beginning of the study, and after any revisions are completed for new information.

- 5) If informed consent is initially given by a subject's legally acceptable representative or legal guardian, and the subject subsequently becomes capable of making and communicating his or her informed consent during the study, consent must additionally be obtained from the subject.
- 6) Revise the informed consent whenever important new information becomes available that is relevant to the subject's consent. The investigator, or a person designated by the investigator, should fully inform the subject or the subject's legally acceptable representative or legal guardian, of all pertinent aspects of the study and of any new information relevant to the subject's willingness to continue participation in the study. This communication should be documented.

The confidentiality of records that could identify subjects must be protected, respecting the privacy and confidentiality rules applicable to regulatory requirements, the subjects' signed ICF and, in the US, the subjects' signed HIPAA Authorization.

The consent form must also include a statement that BMS and regulatory authorities have direct access to subject records.

The rights, safety, and well-being of the study subjects are the most important considerations and should prevail over interests of science and society.

3 INVESTIGATIONAL PLAN

3.1 Study Design and Duration

This is an open label, multi-center, phase 1/2 trial to investigate the safety and efficacy of nivolumab as a single agent or in combination with either ipilimumab, BMS-986016 (relatlimab, anti-LAG3 antibody), or daratumumab in viral positive and viral negative tumor types of the following tumor types: Epstein Barr Virus (EBV) positive gastric cancer, EBV positive nasopharyngeal cancer (NPC), cervical cancer, HPV positive and negative squamous cell cancer of the head and neck (SCCHN), anogenital HPV associated cancers (vaginal, vulvar, anal canal, penile), and Polyomavirus positive Merkel cell cancer (pMCC).

On the basis of eligibility and tumor type, patients will be enrolled into the neoadjuvant or recurrent/metastatic monotherapy, or assigned or randomized into the recurrent/metastatic combination therapies cohorts (A, B, and D). Upon approval of Revised Protocol 05, all Metastatic Combination Cohorts A, B, and D will enroll patients concurrently, and enrollment will be closed for Combination Cohort C.

Combination B SCC of the cervix cohort is being expanded to add approximately 70 patients to further confirm the efficacy signal. Approximately 50 patients will be added to receive Combination B study drug as first-line treatment of their recurrent/metastatic disease if unfit or unsuitable to receive platinum based therapy; and approximately 20 patients will be added to receive study drug as second-line treatment of their recurrent/metastatic SCC of the cervix.

Treatments for each cohort are as follows:

Neoadjuvant cohort:

- Nivolumab administered intravenously (IV) over 30 minutes at 240 mg for 2 doses, on Day 1 and Day 15

Metastatic Monotherapy Cohorts:

- Nivolumab administered IV over 30 minutes at 240 mg every 2 weeks for a maximum of 24 months or until disease progression, unacceptable toxicity, or withdrawal of consent, whichever comes first.

[figure not shown]
Metastatic Combination Cohorts (Combinations A, B, C, and D):

- Combo Arm A: Nivolumab 3 mg/kg IV over 30 minutes every 2 weeks plus Ipilimumab 1 mg/kg IV over 30 minutes every 6 weeks for a maximum of 24 months or until disease progression, unacceptable toxicity, or withdrawal of consent, whichever comes first.
- Combo Arm B: Nivolumab 1 mg/kg IV over 30 minutes plus Ipilimumab 3 mg/kg IV over 30 minutes every 3 weeks for 4 doses followed by Nivolumab 240 mg IV over 30 minutes every 2 weeks for a maximum of 24 months or until disease progression, unacceptable toxicity, or withdrawal of consent, whichever comes first.
- Combo Arm C: Nivolumab 240 mg over 30 minutes every 2 weeks plus Anti-Lag3 (BMS-986016) 80 mg for a maximum of 24 months or until disease progression, unacceptable toxicity, or withdrawal of consent, whichever comes first.
- Combo Arm D: Daratumumab 16 mg/kg IV administered weekly for the first 8 weeks. Starting at Week 3, nivolumab 240 mg IV over 30 minutes will be administered every 2 weeks. Nivolumab will be administered before the daratumumab infusion on study days when both study drugs are administered on the same day. Daratumumab 16 mg/kg will be administered every 2 weeks from Weeks 9-24. Starting at Week 25, nivolumab 480 mg IV flat dose over 30 minutes every 4 weeks; daratumumab 16 mg/kg every 4 weeks for a maximum of 24 months or until progression, unacceptable toxicity, or withdrawal of consent, whichever comes first. The infusion rates for the first, second, and subsequent daratumumab infusions should closely follow the specifications of the currently approved (USPI)/pharmacy reference manual.¹⁸⁴

The tumor types for the neoadjuvant cohort and the study design schematic for the neoadjuvant cohort ([Figure 3.1-1](#)) are presented below:

- HPV positive SCCHN and HPV negative SCCHN
- Cervical, Vaginal, Vulvar carcinoma
- Merkel Cell Carcinoma

[figure not shown]
Figure 3.1-1: Study Design Schematic for the Neoadjuvant Cohort:

The diseases or tumor types for the recurrent/metastatic monotherapy cohort and the study design schematic for the recurrent/metastatic monotherapy cohort is presented in Figure 3.1-2 are presented below:

- EBV positive Gastric cancer,
- HPV positive SCCHN
- Cervical, vaginal, and vulvar carcinoma
- Merkel Cell carcinoma
- Nasopharyngeal Carcinoma (NPC)

Figure 3.1-2: Study Design Schematic for the Metastatic Monotherapy Cohort

The diseases or tumor types for the recurrent/metastatic combination therapy cohorts (Combo A, B and C) are listed below and the study design schematics for the recurrent/metastatic combination therapies A, B, and C are presented in Figure 3.1-3 and Figure 3.1-4.

- HPV positive SCCHN
- Immuno-Oncology naive (anti-tumor vaccine and any T cell co-stimulation or checkpoint pathways therapy) (Combo A)
- Prior PD-1/PD-L1 (Combo C)
- Cervical cancer (Combo A and B)
- Anogenital HPV associated tumors (vaginal, vulvar, anal canal, penile) (Combo A and B)
- Merkel Cell Carcinoma (Combo A)
- Nasopharyngeal Carcinoma (NPC) (Combo A)

Figure 3.1-3: Study Design Schematic for the Metastatic Cohort Combination Therapies A and B and Combo B SCC of the Cervix Expansion

[figure not shown]
[figure not shown]

Figure 3.1-4: Study Design Schematic for the Metastatic Cohort Combination Arm C

*Prior I-O therapy is permitted and is not counted toward the number of prior systemic treatment

**Include subjects that have had prior exposure to anti-PD-1, anti-PD-L1 or anti-CTLA-4 antibodies monotherapy or combination therapy

The disease or tumor type for the recurrent/metastatic combination D therapy cohort are listed below and the study design schematic for the recurrent/metastatic combination cohort for combination therapy D is presented in [Figure 3.1-5](#): HPV positive or HPV negative or unknown SCCHN

- Immuno-Oncology therapy naive (anti-tumor vaccine and any T cell co-stimulation or checkpoint pathways therapy)

Figure 3.1-5: Study Design Schematic for the Metastatic Cohort Combination Therapy D: Tumor Type SCCHN HPV positive, negative or unknown I-O naïve.

[figure not shown]

Table 3.1-1: Tumor Types by Cohort

| Tumor Type | Cohort |
|---|---------------------------------|
| • GYN (cervical, vaginal, vulvar) | |
| • MCC | Neoadjuvant Cohort |
| • HPV (+) SCCHN | |
| • HPV (-) SCCHN | |
| • EBV (+) Gastric | |
| • HPV(+) SCCHN | |
| • GYN (cervical, vaginal, vulvar) | Metastatic Monotherapy Cohort |
| • MCC | |
| • NPC | |
| • MCC | Metastatic Combination Cohort A |
| • HPV+ SCCHN | |
| • NPC | |
| • Cervical cancer | |
| • Other anogenital cancers (vulvar/vaginal/anal/penile) | |
| • Cervical cancer | Metastatic Combination Cohort B |
| • Other Anogenital Cancers (vulvar/vaginal/anal canal/penile) | |
| • HPV+ SCCHN (I-O experienced) | Metastatic Combination Cohort C |
| • HPV +/HPV – or unknown SCCHN (I-O naïve) | Metastatic Combination Cohort D |

All subjects will complete 3 periods of the study: **Screening, Treatment, Follow-up**, including survival follow-up.

Duration of Study: The last visit will be defined as the latest survival visit included in the final analysis of OS (ie, the latest subject death, loss to follow up, or withdrawal of consent) for a tumor type within each cohort. Additional survival follow-up may continue for up to 5 years from the time of this analysis. The study will end once survival follow-up collection has concluded.

3.1.1 Viral Status Determination Prior to Entry

The study will enroll prospective subjects diagnosed with gastric cancer in the Metastatic Monotherapy Cohort. Gastric subjects will provide pre-screening informed consent for determination of EBV+ viral status during the screening period and be registered in IRT. Viral testing will be performed locally or by a central laboratory and test results will be collected. After positive test result confirmation, consent for demographic and further eligibility will be collected. Subjects with EBV negative gastric cancer will be considered screen failures and will not be eligible for the study.

The study will enroll prospective subjects diagnosed with SCCHN. SCCHN subjects will provide consent, via pre-screening informed consent, for determination of HPV viral status, if prior results are not available during the screening period and be registered in IRT (Combo A and C). Viral testing will be performed locally or by a central laboratory and test results will be collected. After viral test result is confirmed positive, consent for demographic and further eligibility will be collected. If subjects decline pre-screening informed consent or are unwilling to undergo viral testing, they are eligible to enroll in Combo D. However, viral status should be determined retrospectively.

The requirement for viral status for each tumor type by cohort is described below and in [Table 3.1.1-1](#).

Neoadjuvant cohort: Confirmation of viral status is required prior to study drug assignment for SCCHN subjects enrolled. Viral testing determined more than 35 days prior to first dose may be used. For SCCHN tumor types in the neoadjuvant cohort, 21 evaluable subjects with virus positive disease and 21 evaluable subjects with virus negative disease will be enrolled. No prior screening for Gyn (cervical, vaginal, vulvar) or MCC cohorts is necessary due to the high prevalence of viral positivity and the technical aspects of the MCPyV assay. Viral positivity will be tested retrospectively for MCC and Gyn tumor types.

Metastatic monotherapy cohort: Gastric and SCCHN subjects will be tested for viral status prior to study drug assignment. Gastric subjects must be EBV positive, and SCCHN subjects must be HPV positive to enroll in this cohort. MCC, NPC, and Gyn (cervical, vaginal, vulvar) subjects will not require viral screening prior to study entry. With the exception of gastric cancer (n=12), each specific tumor type in the metastatic monotherapy cohort will contain 23 subjects. Subjects will be treated with nivolumab 240 mg IV every 2 weeks until disease progression, unacceptable toxicity, or 24 months of treatment. Viral positivity will be tested retrospectively for MCC, NPC, and Gyn tumor types.

Metastatic combination therapy cohort - Combo A, Combo B, and Combo C: SCCHN subjects will be tested for HPV viral status prior to study drug assignment. Viral positivity will be

tested retrospectively for subjects with MCC, NPC, cervical cancer and anogenital HPV associated tumors (vaginal, vulvar, anal canal, and penile); confirmation of viral positivity will not require viral screening prior to study entry.

Approximately 40 subjects with each of the following tumor types will be enrolled into **Combo A and Combo B** into a 1:1 ratio: cervical cancer and anogenital HPV associated tumors (vaginal, vulvar, anal canal, and penile). Additionally, 40 subjects with each of the following tumor types will be enrolled into **Combo A**: MCC, HPV+ SCCHN, and NPC. With Revised Protocol 06, no new subjects will be randomized in the anogenital HPV associated tumors cohorts.

Approximately 40 subjects with SCCHN [prior anti-PD-1 or anti-PD-L1 antibody therapy] will be enrolled into **Combo C**. As of Revised Protocol 05, enrollment will close.

Combo D: Approximately 40 subjects with HPV positive, negative or unknown SCCHN [I-O naive] will be enrolled into **Combo D**. On 26-May-2018 enrollment was closed. Subsequently, the administration of daratumumab in combination with nivolumab was terminated.

Table 3.1.1-1: Testing for Viral Status Prior to Treatment

| Cohort | Tumor Type | Viral status required prior to study drug (Testing) |
|--------------------------------|---|---|
| Neoadjuvant | SCCHN | YES (p16 IHC) |
| | Gyn | NO |
| | MCC | NO |
| Metastatic Monotherapy | EBV+ Gastric | Yes In situ hybridization EBV RNA (EBER) |
| | HPV+/- SCCHN | YES (p16 IHC) (except for Combo D) |
| Metastatic Combination Therapy | Cervical and other HPV associated anogenital tumors (vulvar, vaginal, anal canal, penile) | NO |
| | MCC | NO |
| | NPC | NO |
| | Gyn = cervical, vaginal, vulvar | |

HPV positive, negative or unknown, I-O naive SCCHN patients may participate in Combo D

All subjects (if clinically feasible) in each cohort will receive pre-treatment and on-treatment tumor biopsies. Primary analysis for the Neoadjuvant, Metastatic monotherapy, and Metastatic combination therapy cohorts will be conducted separately after a minimum of at least six months after the first treatment of the last patient for a tumor type enrolled in each cohort. All analyses will be performed independently by cohort and by tumor type.

3.1.2 Neoadjuvant Cohort

The primary objective of the neoadjuvant cohort is to evaluate the safety and tolerability of neoadjuvant nivolumab administration in subjects with select tumor types.

For subjects in the neoadjuvant cohort, radiographic tumor assessments will occur at the following time points (see [Table 5.4.1-2](#)).

- Screening to ensure the subject has resectable disease.
- Within 7 days and prior to the planned surgery or chemotherapy/radiation
- Post-surgery (SCCHN, MCC, Gyn) or post-chemotherapy/radiation (Gyn cohort when appropriate) at indicated Follow-Up visit times.

All subjects must have tumor amenable to pre-treatment biopsy (core needle); post-treatment biopsy will consist of the operative specimen or core needle biopsy for the cervical/vaginal/vulvar subjects.

Treatment within the **neoadjuvant** cohort will consist of:

- A pre-treatment, core-needle, biopsy for all subjects. (Four core-needle biopsies, as described in the laboratory manual, are suggested.)
- Two doses of nivolumab will be administered at 240 mg IV on Day 1 and Day 15
- Surgical resections (SCCHN, MCC, Gyn), or biopsy followed by chemotherapy/radiation (where appropriate for Gyn patients only) will occur on Day 29 (\pm 7 days). No other pre-surgical therapy is allowed.
- After neoadjuvant nivolumab treatment followed by surgical resection or biopsy, subjects will receive standard of care (observation, chemo and/or RT, according to physician's choice).
- Subjects who develop unresectable recurrent or metastatic disease within 1 year of surgery or chemotherapy/radiation completion may receive nivolumab at 240 mg IV every 2 weeks until 24 months of treatment, toxicity, or disease progression, if medically eligible, ie, meet eligibility criteria for metastatic cohort. Written approval from the sponsor's medical monitor is required for subject to be considered eligible. Nivolumab can be administered no earlier than 4 weeks after the last standard of care treatment.
- Enrollment for each tumor type in the neoadjuvant cohort will pause after the first 10 subjects are treated to assess safety and determine the number of subjects with chemotherapy/radiation or surgical delays beyond 4 weeks from the planned surgery date or planned start date for chemoradiation. If \geq 3 of the first 10 subjects for a single tumor type have delays beyond 4 weeks from the planned surgery date or planned start date for chemoradiation due to a nivolumab immune-related adverse event(s) specified in the label in the region of treatment, that specific tumor cohort will close. The remaining tumor types in the neoadjuvant cohort will not close enrollment should a tumor type(s) close due to a delay in surgery due to nivolumab. If the first 8 patients treated for a single tumor type experience no delay, a pause in enrollment will not be required.

Details regarding the procedures associated with the neoadjuvant cohort can be found in [Table 5.1-4](#). Details regarding procedures required for subjects who develop unresectable recurrent or metastatic disease within 1 year of surgery or chemotherapy/radiation and receive nivolumab can be found in [Table 5.1-2](#).

3.1.3 *Subjects in the Metastatic Monotherapy Cohort*

For subjects without resectable disease, nivolumab will be administered at 240 mg every 2 weeks until toxicity, disease progression, withdrawal of consent, or 24 months of treatment, whichever comes first. For subjects in the metastatic cohort, radiographic tumor assessments by CT (preferred)/MRI will begin 8 weeks (\pm 1 week) after the start of therapy and will continue every 8 weeks (\pm 1 week) for the first year of treatment. CT (preferred)/MRI will continue every 12 weeks (\pm 2 weeks) for the second year and beyond. Tumor assessments will follow the above schedule until disease progression is documented. If the subject discontinues treatment prior to disease progression, tumor assessment will continue per protocol as described in [Table 5.4.1-1](#). Disease progression is defined by investigator-assessed RECIST 1.1 criteria. The primary endpoint of this cohort is objective response rate (ORR) based on investigator assessments, using RECIST 1.1 criteria. Exploratory endpoints include complete and partial remission rates and durations based on radiological assessments. Individual tumors types will be analyzed separate from each other.

In all subjects for each tumor type, biopsy and submission of fresh tumor tissue, or submission of archived tumor tissue, is mandatory for all subjects. Subjects with accessible lesions where biopsy is deemed safe by the Investigator should undergo biopsy per protocol.

3.1.4 *Subjects in the Metastatic Combination Cohorts*

Upon approval of Revised Protocol 05, all Metastatic Combination Cohorts A, B, and D will enroll patients concurrently, and enrollment in Cohorts C will be closed.

Subjects with SCCHN, MCC or NPC enrolled in Combo A will be treated with nivolumab 3mg/kg every 2 weeks plus ipilimumab 1mg/kg every 6 weeks (Combo A) for a maximum of 24 months or until disease progression, unacceptable toxicity, or withdrawal of consent, whichever comes first.

Subjects with cervical cancer and anogenital HPV associated tumors (vulvar/vaginal/anal canal/penile) will be randomized (1:1) to treatment with either Combo A - nivolumab 3mg/kg every 2 weeks plus ipilimumab 1mg/kg every 6 weeks or Combo B - nivolumab 1mg/kg plus ipilimumab 3mg/kg every 3 weeks for 4 doses followed by nivolumab 240 mg every 2 weeks for a maximum of 24 months, or until disease progression, unacceptable toxicity, or withdrawal of consent, whichever comes first. With Revised Protocol 06, no new subjects will be randomized in the anogenital HPV associated tumors cohorts.

Subjects with HPV+ SCCHN with prior PD-1/PD-L1 treatment who are enrolled in Metastatic Combination Cohort (Combo C) will be treated with BMS-986016 (relatlimab) 80 mg plus nivolumab 240 mg q2w for a maximum of 24 months until disease progression, unacceptable toxicity, or withdrawal of consent, whichever comes first.

Subjects with HPV negative, positive, or unknown SCCHN who are I-O naive will be enrolled into the metastatic SCCHN Combo D (nivolumab plus daratumumab).

For subjects in the metastatic cohorts, radiographic tumor assessments by CT (preferred)/MRI will begin 8 weeks (\pm 1 week) after the start of therapy and will continue every 8 weeks (\pm 1 week) for the first year of treatment. CT (preferred)/MRI will continue every 12 weeks (\pm 2 weeks) for the second year and beyond. Tumor assessments will follow the above schedule until disease progression is documented. If the subject discontinues treatment prior to disease progression, tumor assessment will continue per protocol as described in [Table 5.4.1-1](#). Study treatment will be administered until unacceptable toxicity, 24 months of treatment, or disease progression which is defined by investigator assessed RECIST 1.1 criteria. The primary endpoint of this cohort is objective response rate (ORR) based on investigator assessments, using RECIST 1.1 criteria. Exploratory endpoints include complete and partial remission rates and durations based on radiological assessments. Individual tumors types will be analyzed separate from each other.

In all subjects for each tumor type, biopsy and submission of fresh tumor tissue, or submission of archived tumor tissue, is mandatory for all subjects. Subjects with accessible lesions where biopsy is deemed safe by the Investigator should undergo biopsy per protocol.

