checkpoint inhibition has been established in a Phase I bladder cancer study with ipilimumab (see [Section 1.1.3](#)). In addition, to minimize the risk of potential delays, a two stage approach will be taken to stop enrollment if there are delays to surgery or chemotherapy/radiation due to a nivolumab-related adverse event as specified in the label in the region of treatment in more than 2 of the first 10 subjects treated within each tumor type. Lastly, although there are no efficacy data on neoadjuvant administration of nivolumab, there is potential for some clinical benefit as objective responses have been observed in clinical trials within weeks of initial treatment.

There is risk associated with tumor biopsies, including bleeding, infection, and pain. While there is no direct benefit to subjects who undergo these procedures, there is a potential that data generated from these samples will guide the further development of these compounds and may be of direct benefit for others with advanced solid tumors.

In summary, based on the manageable safety profile of nivolumab and nivolumab in combination with ipilimumab, the observed clinical activity of nivolumab and nivolumab in combination with ipilimumab across multiple tumor types, and the rationale for immune checkpoint inhibition for patients with virus-associated tumors, it is felt that the overall benefits to subjects outweigh the potential risks in the neoadjuvant or metastatic/recurrent settings. Furthermore, the potential direct benefit to subjects who participate in this study of combined therapy with nivolumab plus relatlimab may result in a greater proportion of subjects with stabilization of disease, objective response, or increased duration of response than those observed with nivolumab monotherapy. It is also possible that combination therapy may reverse LAG-3-mediated T cell exhaustion and achieve responses in virus-associated tumors.

Additionally, because nivolumab and daratumumab have some overlapping toxicity profiles (i.e. infusion related reaction, diarrhea), it is possible that a higher incidence of adverse events may occur with the combination of 2 drugs. Based on the above assessment, the potential benefit of combining nivolumab and daratumumab appears to outweigh the potential risk. The overall risk/benefit assessment supports the evaluation of these combinations in this setting. Per Revised Protocol 06, enrollment and treatment in this cohort have been terminated.

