8.3 Endpoints

8.3.1 Primary Endpoint(s)

Neoadjuvant cohort:

- The safety and tolerability objective will be measured by the incidence of drug-related select AEs and drug-related SAEs.
- Rate of surgery delay, which is defined as the proportion of subjects in the neoadjuvant cohort with surgery delayed > 4 weeks from the planned surgery date or planned start date for chemoradiation due to a drug-related AE will be reported for each tumor type.

Metastatic cohorts (monotherapy and combination therapies):

- The investigator-assessed objective response rate (ORR). ORR is defined as the number of subjects with a best overall response (BOR) of confirmed complete response (CR) or partial response (PR) divided by the number of treated subjects. BOR is defined as the best response designation recorded between the date of first dose and the date of the initial objectively documented tumor progression per investigator assessment using RECIST 1.1 criteria or the date of the last tumor assessment date prior to subsequent therapy. In this study, an ORR in excess of 10% will be considered of clinical interest, and an ORR of 25% or greater will be considered of strong clinical interest.

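### The neoadjuvant 3-of-10 closure rule is worded differently in Protocol 1.5 and 3.1.2, and under 3.1.2 it counts fewer delays than the primary endpoint

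*Protocol*

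**What the plan says.** Three current passages define the delay event.

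- **Protocol 3.1.2 (the operative rule).** A tumor type closes if 3 or more "of the first 10 subjects for a single tumor type have delays beyond 4 weeks from the planned surgery date", or from the planned chemoradiation start, and the delay is "due to a nivolumab immune-related adverse event(s) specified in the label in the region of treatment, that specific tumor cohort will close". To count, an event must be immune-related and listed in the label where the subject is treated.
- **Protocol 1.5 (risk/benefit).** Enrollment stops for delays "due to a nivolumab-related adverse event as specified in the label in the region of treatment in more than 2 of the first 10 subjects", counted separately for each tumor type. The threshold is the same, since more than 2 means 3 or more. The event need not be immune-related, and that sentence gives no minimum length of delay.
- **Protocol 8.3.1 (primary endpoint, repeated in SAP 4.1.1).** The rate of surgery delay is the proportion with "surgery delayed > 4 weeks from the planned surgery date or planned start date for chemoradiation due to a drug-related AE". There is no immune, label or region limit.

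Two other parts of 3.1.2 are broader than its closure count. Enrollment "will pause after the first 10 subjects are treated to assess safety and determine the number of subjects with chemotherapy/radiation or surgical delays", and the waiver of that pause reads: "If the first 8 patients treated for a single tumor type experience no delay, a pause in enrollment will not be required". Neither is limited by attribution.

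**The concern.** The cohort's primary objective is safety and tolerability of nivolumab before curative-intent treatment. Section 1.5 gives the purpose of the rule as limiting delays to that treatment. A delay of more than 4 weeks caused by a drug-related event that is unlisted or not immune-related defeats that purpose just as much as one caused by a listed immune event. It counts toward the primary endpoint, but not toward closure under 3.1.2.

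As written, the person running the 10-subject review has two versions of the rule to choose from. Neither matches the endpoint reported for the same subjects. The label qualifier also makes the count depend on where a subject is treated, so identical events could be classified differently within one tumor type.

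**Working it through.** **1. The plan's own figures.** The only probabilities stated for this cohort (Protocol 8.1) are those of seeing at least one event in 21 subjects, 1 − (1 − p)^21:

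- Safety event: p = 5% gives 65.9% (stated as 66%) and p = 10% gives 89.1% (stated as 89%).
- Pathologic complete response: p = 10%, 15% and 20% give 89.1%, 96.7% and 99.1% (stated as 89%, 97% and 99%).

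These reproduce to rounding. No operating characteristics are given for the 3-of-10 rule.

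**2. The definitions side by side.**

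| | Protocol 3.1.2 | Protocol 1.5 | Protocol 8.3.1, SAP 4.1.1 |
|---|---|---|---|
| Attribution | nivolumab, immune-related | nivolumab-related | drug-related |
| In regional label | required | required | not required |
| Delay > 4 weeks | required | not in that sentence | required |
| Use | closes tumor type | describes closure | primary endpoint |

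Every subject counted under 3.1.2 is also an endpoint event, but the reverse need not hold. Three endpoint events in ten subjects, of which one is unlisted or not immune-related, give a closure count of 2 and no automatic closure.

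**3. Is the boundary clear?** Section 1.1.3 lists the most frequent drug-related SAEs in the first 4 weeks of nivolumab monotherapy as pneumonitis (0.33%), pyrexia (0.3%), infusion-related reaction (0.24%) and hypersensitivity reaction (0.12%). Section 3.1.2 does not say whether the last three are immune-related for this purpose. These are SAE rates, not delay rates. They show that classification is ambiguous, not how often it would matter.

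**4. Illustration of size.** Let p be the true rate of > 4-week delays due to any drug-related AE, and f the share of those delays that qualify under 3.1.2. Neither value is in the documents, so both are assumed. The chance that the rule triggers is P(X ≥ 3) with X ~ Binomial(10, p × f), that is, 1 − Σ C(10,k)(pf)^k(1 − pf)^(10−k) for k = 0, 1, 2.

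| p | f = 100% | f = 80% | f = 60% |
|---|---|---|---|
| 5% | 1.2% | 0.6% | 0.3% |
| 10% | 7.0% | 4.0% | 1.9% |
| 20% | 32.2% | 20.6% | 10.9% |
| 30% | 61.7% | 44.4% | 26.3% |

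For example, p = 30% and f = 80% give pf = 0.24, and 1 − (0.064 + 0.203 + 0.288) = 0.44.

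**5. Is there a backstop?** The pause includes a general safety assessment, but no criterion says when delays outside the 3.1.2 count should lead to closure. Protocol section 7 and SAP 2.5 both state that a data monitoring committee is not applicable.

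**The case against.** A closure trigger and an endpoint may legitimately differ. Relatedness is a yes/no physician judgement in an open-label study, and a stricter trigger guards against closing a tumor type on doubtful attribution in ten subjects. That is a defensible design choice, but the documents do not state it as the reason. It also does not explain why 1.5 and 3.1.2 differ.

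Four stronger readings are tempting, and the documents do not support them.

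- *That the plan ignores unlisted toxicity.* Only the automatic closure count is narrow. The pause assesses safety in general, any delay in the first 8 patients blocks the waiver whatever its cause, and section 1.5 provides for ongoing review of AEs and SAEs by the medical monitor, investigators and pharmacovigilance. Section 3.1.2 does not say that its count is the only ground for closing. A tumor type outside the count is not closed automatically, which is different from being required to stay open.
- *That the rule does operate differently by region.* The wording allows this, but the regional labels are not in the documents. Whether any relevant event is listed in one region and not in another cannot be established.
- *That the effect is large in practice.* The wide contrasts appear at delay rates of 20% to 30%. The nearest anchor in the documents is about 3% drug-related SAEs in the first 4 weeks (1.1.3), which also calls significant surgical delay unlikely. An SAE rate is not a delay rate, but at 5% to 10% the absolute differences are small. A stopping rule still has to be judged at the high rates it is meant to catch.
- *That the safety estimate is compromised.* The primary endpoint still counts every > 4-week delay due to a drug-related AE, whatever closure rule is used.

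**Conclusion.** The inconsistency is real. Sections 1.5 and 3.1.2 give two versions of one safety rule, and the version in 3.1.2 counts a subset of the primary endpoint's events without a stated reason. Three or more of the first ten subjects could meet the primary delay endpoint without triggering automatic closure, and no written criterion covers that case.

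The size depends on two assumed quantities. If 60% rather than all of the drug-related delays qualify, the chance of triggering falls from 62% to 26% at a 30% delay rate, from 32% to 11% at 20%, and from 7% to 2% at 10%. If every drug-related delay qualifies, the closure and endpoint counts coincide. The regional difference is a possibility created by the wording and cannot be sized from these documents. No view is taken here on which attribution is right for closure.

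**What to change.** Reconcile Protocol 1.5, 3.1.2 and 8.3.1 and SAP 4.1.1, so that the 3-of-10 count has one stated event definition, including the length of delay. The primary endpoint's definition is one available candidate and needs no new data, because section 6 already requires a causality judgement for every AE. If a narrower closure count is intended, state the reason, use the same wording in 1.5 and 3.1.2, and say how label listing is determined for each subject.

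In either case, report the number of > 4-week delays at each 10-subject review under both the closure and the endpoint definitions. Section 6.2.1 already has the investigator judge whether each AE is immune-mediated. The remaining step is to check the event against the regional label. If these reviews are already past, both counts per tumor type can still be given in the study report.

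The cost is protocol wording and one extra line in the review. If the broader definition is adopted, a tumor type is somewhat more likely to close, by the differences shown in the table.
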